#### 4.7.2.2 Sensitivity Analyses

A sensitivity analysis for OS will examine the censoring patterns to rule out attrition bias with regard to the treatment comparisons, achieved by a Kaplan-Meier plot of time to censoring where the censoring indicator of OS is reversed.

The number of subjects prematurely censored will be summarized by treatment group. A subject would be defined as prematurely censored if their survival status was not defined at the data cut-off (DCO).

Sponsor:	Radius		
Protocol:	RAD1901-308		
Document Version No.:	1.1 (Final)	Document Date:	10-MAY-2021

In addition, duration of follow-up will be summarized using medians:

- x In all subjects: Time from randomization to the date of death (i.e. overall survival) or to the date of censoring (date last known to be alive) for censored subjects regardless of treatment group.
- x By treatment group: Time from randomization to the date of death (i.e. overall survival) or to the date of censoring (date last known to be alive) for censored subjects

To assess potential COVID-19 impact, if subjects died due to COVID-19 infection, OS date will be censored at the death date. Analysis of OS will be performed in the same manner as the primary key secondary analysis if at least 5% of deaths are due to COVID-19 infection.

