### 2.2 Randomization Methodology

The Investigators will randomize eligible subjects by Interactive Randomization Technology (IRT) as described in the IRT User Guide. Eligible subjects will be enrolled into the study and randomized in a 1:1 ratio to receive elacestrant 400 mg tablet once daily (QD) or SOC of either fulvestrant or an AI, stratified by

- x ESR1 mutational status as detected by ctDNA at central laboratory (ESR1-mut vs ESR1-mut-nd)
- x Prior treatment with fulvestrant (yes vs no)
- x Presence of visceral metastasis (yes vs no); visceral includes lung, liver, brain, pleural and peritoneal involvement

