X If the larger p-value is  $< 0.025$ , statistical significance will be claimed only for the endpoint associated with the smaller p-value. An alpha of 0.0025 will be passed along to OS only in the population in which PFS is significant. To control for the 2 different times the OS analysis will be conducted, the alpha level of 0.0025 will be distributed across the 2 time points. An alpha level of 0.0001 will be allocated at the time of the primary PFS analysis and an alpha level of 0.0024 will be allocated at the time of the final OS analysis. This adjustment is according to a Haybittle-Peto rule.

X If the larger p-value is  $\geq 0.025$ , statistical significance will not be claimed. In this case, no alpha will be passed along to OS. No claim regarding OS will be made.

OS will be evaluated at 2 time points: (1) at the time of the primary analysis of PFS and (2) when approximately 50% of all subjects (ESR1-mut and ESR1-mut-nd) have died. At the time of this amendment, the study is fully enrolled (N=478). The second analysis of OS will take place when approximately 239 subjects have died. At the time of the PFS analysis, it is expected that approximately 96 subjects will have died.

Among all subjects (ESR1-mut and ESR1-mut-nd), the study will have 60% power to detect a hazard ratio of 0.75 at a 1-sided alpha level of 2.5%. Assuming a median OS of 25 months for the SOC treatment group, this hazard ratio represents a median OS of 33 months for the elacestrant treatment group. This calculation also accounts for 1 interim analysis at an information fraction of 0.4 with an alpha spending equal to 0.0001 at the interim analysis.

The study has enrolled 228 ESR1-mut subjects. Approximately 114 OS events are expected among the ESR1-mut subjects at the time of the second analysis of OS. With 114 OS events, the study will have 39% power to detect a hazard ratio of 0.73 at a 1-sided alpha level of 2.5%. Assuming a median OS of 28 months for the SOC treatment group, this treatment effect represents a median OS of 38 months for the elacestrant treatment group, an increase of approximately 10 months among the ESR1-mut subjects. This calculation also accounts for 1 interim analysis at an information fraction of 0.4 with an alpha spending equal to 0.0001 at the interim analysis.

Unless otherwise specified, analyses of all other efficacy endpoints will be performed at the 2-sided alpha level of 5% without adjusting the p-values for multiple comparisons.

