#### 4.7.2 Key Secondary Efficacy Endpoints

##### 4.7.2.1 Key Secondary Analysis

Key secondary efficacy endpoints include the following:

- x OS in ESR1-mut subjects
- x OS in all subjects (ESR1-mut and ESR1- mut-nd)

Overall survival is defined as the time from the date of randomization until death due to any cause regardless of whether the subject withdraws from randomized treatment or receives another anticancer therapy (i.e., date of death or censoring – date of randomization + 1). Any subject not known

Sponsor:	Radius		
Protocol:	RAD1901-308		
Document Version No.:	1.1 (Final)	Document Date:	10-MAY-2021

to have died at the time of analysis will be censored based on the last recorded date on which the subject was known to be alive. The last known alive date is the date subject last confirmed to be alive from eCRF Survival Status page.

Analyses of OS in ESR1-mut subjects and in all subjects (ESR1-nut and ESR1- mut-nd) will be performed using the ITT population.

For each of the 2 sets of study subjects, OS will be analyzed at the following 2 time points

- x At the time of the primary PFS analysis (when approximately 160 and 340 PFS events are observed among the ESR1-mut and all subjects (ESR1-mut and ESR1- mut-nd), respectively, and
- x At the time of the final OS analysis (when approximately 50% of the subjects have died)

At each time point, analyses of OS will be conducted in a similar manner as the primary analysis of PFS. Number and percentage of subjects with event and subjects censored will be tabulated by treatment group.

Kaplan-Meier method will be used to estimate the survival distribution function of OS. The following summaries by treatment group will be provided: median OS and 95% CI, 1st and 3rd quartiles and 95% CI, overall survival rates and 95% CI at months 6, 12, and 18 (and every 6 months thereafter until the end of follow-up or no more subjects are at risk).

The difference in the key secondary endpoints between the 2 treatment groups will be analyzed using the stratified log-rank test, with the randomization stratification factors (as described in section [4.7](#)) for generation of the p-value.

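### The planned median OS follow-up counts death as the end of follow-up, so it understates follow-up and runs shorter in the arm with more deaths

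*SAP*

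**What the plan says.** The OS sensitivity section (SAP 4.7.2.2) contains three descriptive items that matter here.

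- **Censoring pattern.** Attrition bias is to be examined by a "Kaplan-Meier plot of time to censoring where the censoring indicator of OS is reversed". This is a reverse Kaplan-Meier curve. No median is taken from it.
- **Premature censoring.** Subjects whose survival status is unknown at the data cut-off are counted by treatment group.
- **Follow-up.** "In addition, duration of follow-up will be summarized using medians". The quantity, overall and by arm, is "Time from randomization to the date of death (i.e. overall survival) or to the date of censoring (date last known to be alive"). It is not restricted to survivors, and no other follow-up measure is defined.

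The censoring date matches the OS endpoint in SAP 4.7.2.1, where subjects not known to have died are "censored based on the last recorded date on which the subject was known to be alive". The follow-up variable is therefore the OS analysis time itself, with deaths and censored times pooled into one plain median.

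**The concern.** Follow-up duration should say how long subjects could have been observed. A subject who dies at month 6 in a trial with a 30-month observation window contributes 6 months to the planned median. The more deaths there are, the shorter the reported follow-up, so the figure mixes the outcome with the maturity of the data.

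The by-arm version has a further problem. If elacestrant prolongs survival, its subjects will show longer follow-up than SOC subjects with identical entry dates, cut-off and loss. A reader who uses the two medians to check for unequal follow-up would see an imbalance produced by mortality. That is awkward in a section meant to rule out attrition bias between arms.

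**Working it through.** **Inputs.** SAP 4.2.6: enrollment closed at 478 subjects; final OS analysis at about 239 deaths; about 96 deaths at the PFS analysis; median OS 25 months (SOC) and 33 months (elacestrant). SAP 2.2: 1:1 allocation, so 239 per arm. Protocol 11.3.5: 15-month enrollment. Assumed because the documents are silent: exponential survival, uniform accrual, accrual of 20 and 24 months as alternatives, and loss to follow-up of 0 or 0.5% per month.

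**Check of the OS inputs.** The documents give no follow-up figure to reproduce, but they give OS power. With power = Φ(½·√D·|ln HR| − 1.96):
- All subjects: ½·√239·|ln 0.75| = 2.224; Φ(0.264) = 60.4%, against 60% stated.
- ESR1-mut: ½·√114·|ln 0.73| = 1.680; Φ(−0.280) = 39.0%, against 39% stated.

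**Closed-form case: final OS analysis, 15-month accrual, no loss.**
1. At a cut-off 36.4 months after the first randomization, the expected death proportions are 0.548 (SOC) and 0.453 (elacestrant). Expected deaths are 239 × (0.548 + 0.453) ≈ 239, as planned.
2. Potential follow-up is then uniform from 21.4 to 36.4 months, with median 28.9 in both arms. Reverse Kaplan-Meier estimates this.
3. The planned statistic is the t at which S(t) × (36.4 − t)/15 = 0.5, with S(t) = 2^(−t/median OS).
   - Overall, t = 23.2: mean S = 0.570; 0.570 × 0.880 = 0.50.
   - SOC, t = 22.4: 0.537 × 0.933 = 0.50.
   - Elacestrant, t = 24.0: 0.604 × 0.827 = 0.50.

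The understatement is 28.9 − 23.2 = 5.7 months. The arm gap is 24.0 − 22.4 = 1.6 months, although follow-up is identical.

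**Simulation, final OS analysis (239 deaths, 400 trials per setting), months.**

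| Accrual | Loss/month | Planned, all | Elacestrant | SOC | Arm gap | Reverse KM, all |
|---|---|---|---|---|---|---|
| 15 | 0 | 23.2 | 24.0 | 22.5 | 1.5 | 28.9 |
| 15 | 0.5% | 23.4 | 24.8 | 21.2 | 3.6 | 30.6 |
| 20 | 0 | 22.0 | 22.9 | 21.2 | 1.7 | 29.0 |
| 20 | 0.5% | 22.7 | 23.8 | 21.0 | 2.8 | 30.7 |
| 24 | 0 | 21.1 | 22.0 | 20.2 | 1.8 | 29.1 |
| 24 | 0.5% | 21.8 | 22.9 | 20.5 | 2.4 | 30.5 |

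Reverse Kaplan-Meier agreed between arms to within 0.1 month in every row. Repeat simulations of the first row gave 22.2 to 22.5 for SOC, 23.8 to 24.0 for elacestrant and 28.6 to 28.9 by reverse Kaplan-Meier. Across the whole grid, repeats gave 21.0 to 23.5 for the planned statistic, 28.6 to 30.9 for reverse Kaplan-Meier and arm gaps up to 3.9.

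**ESR1-mut** (114 deaths, medians 28 and 38, 15-month accrual, no loss): 27.0 overall (27.9 elacestrant, 25.9 SOC), against 32.7.

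**PFS analysis** (96 deaths, 15-month accrual, no loss): 7.8 overall (8.0 elacestrant, 7.6 SOC), against 9.4. Only 15-month accrual fits this look, because with 20 or 24 months the 96th death would fall before enrollment ended.

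**Equal hazards** (25 months in both arms, 239 deaths): 19.7 and 19.8 by arm, against 25.2. The arm gap disappears and the understatement remains.

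**The case against.** The best defence is that the SAP defines the quantity openly. As a description of time actually observed it is valid, since a subject who has died is completely observed for OS. The fault then lies in the label. This is largely right: the number is not miscalculated, it is presented as follow-up when it measures something else. The defence does not remove the dependence on each arm's mortality, which makes the by-arm comparison misleading.

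A second defence is that attrition is covered elsewhere in the same section, by the reverse curve and the premature-censoring count. This stands. A reader might infer that the plan has no means of detecting unequal censoring, and the documents do not support that. What is missing is only the printed median and interval from the curve.

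A third is that OS maturity is set by the death count: the final analysis is triggered at about 239 deaths, and events and censored subjects are tabulated by arm. This also stands, and it limits the weight of the point.

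The months shown depend on assumptions. The documents give no loss rate, and accrual beyond 15 months is assumed. The PFS-look figures are fixed by 96 deaths, which these inputs place about 17 months after the first randomization, whereas SAP 4.1 expects that analysis at 30 to 33 months. They illustrate the mechanism and do not forecast the report.

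**Conclusion.** The point holds as a reporting matter of low severity. Under the SAP's OS assumptions, the planned median understates follow-up at the final OS analysis by roughly 5.5 to 9 months (about 20 to 30%) and creates an arm difference where none exists. At the PFS analysis the shortfall is about 1.6 months. The direction does not depend on the assumed accrual, loss or survival shape: any deaths before the cut-off pull the median down or leave it unchanged, and higher mortality in one arm shortens that arm's figure. The sizes do depend on them.

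A reader might go further and infer that the OS comparison is biased. The documents do not support that. The statistic enters no log-rank test, Cox model, alpha allocation or power calculation, and OS itself is censored in the usual way. The arm gap is also not inevitable, since it vanishes if survival is the same in both arms.

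**What to change.** In SAP 4.7.2.2, replace the two follow-up definitions with one sentence: median follow-up, with 95% CI, will be estimated overall and by treatment group from the reverse Kaplan-Meier curve, with deaths treated as censored and OS censoring treated as the event. If the present statistic is kept, label it observed time on study.

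The cost is a wording change and one extra line of output. The curve is already planned, and no new data or model is needed. Where there is loss to follow-up, reverse Kaplan-Meier will sit below potential follow-up (for example 30.6 against 31.9 months at 15-month accrual and 0.5% loss per month). This is proper, because that time really was lost.

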#### 4.7.2.3 Restricted Mean Survival Time Analyses

Restricted mean survival time analysis will be provided for the key secondary efficacy endpoints in a similar manner as IRC-assessed PFS as described in Section [4.7.1.4](#) as a supportive analysis.

#### 4.7.3 Other Secondary Efficacy Endpoints

The following secondary efficacy endpoints will be assessed in ESR1- mut-nd subjects

- x IRC-assessed PFS
- x OS

The following secondary efficacy endpoints will be assessed for ESR1-mut subjects, ESR1- mut-nd subjects, and All (ESR1-mut and ESR1- mut-nd) subjects:

- x Local Investigator-assessed PFS
- x IRC-assessed ORR and DoR
- x IRC-assessed CBR
- x Local Investigator-assessed ORR and DoR
- x Local Investigator-assessed CBR

Analyses of IRC-assessed PFS in ESR1- mut-nd subjects will be performed using the ITT population for the ESR1- mut-nd subjects, in the same manner as the analyses of the primary efficacy endpoints.

Analyses of OS in ESR1- mut-nd subjects will be performed using the ITT population for the ESR1- mut-nd subjects, in the same manner as the analyses of OS in ESR1-mut subjects and all subjects (ESR1-mut and ESR1- mut-nd).

Sponsor:	Radius		
Protocol:	RAD1901-308		
Document Version No.:	1.1 (Final)	Document Date:	10-MAY-2021

#### 4.7.3.1 Local Investigator-assessed PFS

PFS will also be derived based on local investigator assessment, in the same way as the derivation of the primary endpoints and will be analyzed using the ITT population for ESR1-mut subjects, ESR1- mut-nd subjects, and all subjects (ESR1-mut and ESR1- mut-nd), in the same manner as the primary and secondary analyses.

#### 4.7.3.2 IRC-assessed Objective Response Rate (ORR)

Independent Review Committee-assessed ORR is defined as the percentage of subjects whose best overall response (BOR) was either complete response (CR) or partial response (PR), where BOR will be derived using blinded IRC assessment following the RECIST (version 1.1) criteria. For each subject, BOR can be 1 and only 1 of the following: CR, PR, stable disease (SD), progressive disease (PD) and not evaluable (NE), with derivation using the order of CR > PR > SD > PD > NE. Additionally, the response of CR or PR will require confirmation at least 4 weeks after the initial documentation of the response. When confirmation is required, BOR is derived according to Table 3 below. Responses recorded after initiation of new systemic anti-cancer therapy will be excluded from BOR derivation.

#### 4.7.3.4 IRC-assessed Clinical Benefit Rate (CBR)

Independent Review Committee-assessed CBR will be summarized using the CBE population (based on IRC assessment) for ESR1-mut subjects, ESR1- mut-nd subjects, and all subjects (ESR1-mut and ESR1- mut-nd). CBR is defined as the proportion of subjects who had confirmed CR or PR any time during the study, or SD that lasted at least 24 weeks (including disease assessments performed up to a week earlier than the scheduled date). The IRC-assessed CBR will be derived based on the blinded IRC assessment and will be analyzed in the same manner as the analysis of ORR.

#### 4.7.3.5 Local Investigator-assessed ORR and DoR

Objective Response Rate will be derived from tumor assessments performed by Local Investigators using the RECIST criteria and analyzed in the same manner as the analysis of IRC-assessed ORR.

Sponsor:	Radius		
Protocol:	RAD1901-308		
Document Version No.:	1.1 (Final)	Document Date:	10-MAY-2021

Local Investigator-assessed DoR will be derived and analyzed in the same manner as the IRC-assessed DoR.

Analyses of local Investigator-assessed ORR and DoR will be provided for the RE population (based on Local Investigator assessment) for ESR1-mut subjects, ESR1- mut-nd subjects, and all subjects (ESR1-mut and ESR1- mut-nd).

#### 4.7.3.6 Local Investigator-assessed CBR

The Local Investigator-assessed CBR will be derived based on Local Investigator assessment, similar to the derivation of the IRC-assessed CBR and analyzed in the same manner for CBE population (based on Local Investigator assessment) for ESR1-mut subjects, ESR1- mut-nd subjects, and all subjects (ESR1-mut and ESR1- mut-nd).

#### 4.8 Patient Reported Outcomes (PROs)

PRO endpoints are secondary endpoints and will be summarized by treatment group using the ITT population for ESR1-mut subjects and all subjects (ESR1-mut and ESR1- mut-nd).

##### 4.8.1 EQ-5D-5L

The EQ-5D-5L will be used to explore the impact of treatment and disease state on health state utility.

The EQ-5D-5L, developed by the EuroQol Group, is a generic questionnaire that provides a simple descriptive profile of health and a single index value for health status for economic appraisal. The EQ-5D-5L questionnaire comprises 6 questions that cover 5 dimensions of health (mobility, self-care, usual activities, pain/discomfort and anxiety/depression). For each dimension, respondents select which statement best describes their health on that day from a possible 5 options of increasing levels of severity (no problems, slight problems, moderate problems, severe problems and unable to/extreme problems). A unique EQ-5D health state, termed the EQ-5D-5L profile, is reported as a 5-digit code with a possible 3,125 health states. For example, state 11111 indicates no problems on any of the 5 dimensions. Respondents also assess their health on that day using the EQ-VAS, which ranges from 0 (worst imaginable health) to 100 (best imaginable health).

The EQ-5D profile will be converted into a weighted health state utility value, termed the EQ-5D index, by applying a country-specific equation to the EQ-5D-5L profile that represents the comparative value of health states. This equation is based on national valuation sets elicited from the general population and the base case will be the UK perspective. Where a valuation set has not been published, the EQ-5D-5L profile will be converted to the EQ-5D index using a crosswalk algorithm ([van Hout et al. 2012](#)). The EQ-VAS is reported separately.

Descriptive statistics will be calculated for each scheduled visit/time point in the study, for each study drug, and as a total. This will report the number of subjects, the number of EQ-5D questionnaires completed for each visit, and the number and proportion of subjects responding to each dimension of the EQ-5D-5L. Additionally, summary statistics (eg, n, mean, median, SD, min, and max) will be reported for the EQ-5D index score and the EQ-VAS score, and the change from baseline will be reported for the EQ-5D index score and the EQ-VAS score.

Graphical plots of the mean (+/- standard deviation) EQ-5D index score and EQ-VAS score, including change from baseline by scheduled visits/time points in the study may be produced.

##### 4.8.2 EORTC-QLQ-C30

The EORTC QLQ-C30 consists of 30 questions that can be combined to produce 5 functional scales (physical, role, cognitive, emotional, and social), 3 symptom scales (fatigue, pain, and nausea/vomiting), and global health status/QoL scale. The EORTC QLQ-C30 will be scored according to the EORTC QLQ-C30 Scoring Manual ([Fayers et al. 2001](#)). An outcome variable consisting of a score from 0 to 100 will be derived for each of the symptom scales, each of the functional scales, and the global measure of health status scale in the EORTC QLQ-C30 according to the EORTC QLQ-C30 Scoring Manual. Higher scores on

Sponsor:	Radius		
Protocol:	RAD1901-308		
Document Version No.:	1.1 (Final)	Document Date:	10-MAY-2021

the global measure of health status and functional scales indicate better health status/function, but higher scores on symptom scales represent greater symptom severity.

Patient-reported outcome (PRO), based on scales from the QLQ-C30 questionnaires, will be summarized at Cycle 1 Day 1 (i.e., baseline) and each time it is measured according to the protocol schedule, along with change from baseline (CFB). Line graph presentation of arithmetic mean ( $\pm$ standard deviation) plots of scores and change from baseline versus time point will be produced.

The following scores will be calculated: 5 functional scales, 3 symptom scales, a global health status/quality of life (QoL) scale, and 6 single items, Table 4.

**Table 4 EORTC QLQ-30 Scales and Items**

Scale/Item	Label	Items (Questions) included	Range of response for items
Global Health Status / QOL	QL2	29, 30	6
Functional Scales			
Physical functioning	PF2	1 - 5	3
Role functioning	RF2	6, 7	3
Emotional functioning	EF	21 - 24	3
Cognitive functioning	CF	20, 25	3
Social functioning	SF	26, 27	3
Symptom Scales/Items			
Fatigue	FA	10, 12, 18	3
Nausea and vomiting	NV	14, 15	3
Pain	PA	9, 19	3
Dyspnea	DY	8	3
Insomnia	SL	11	3

Sponsor:	Radius		
Protocol:	RAD1901-308		
Document Version No.:	1.1 (Final)	Document Date:	10-MAY-2021

Scale/Item	Label	Items (Questions) included	Range of response for items
Appetite loss	AP	13	3
Constipation	CO	16	3
Diarrhea	DI	17	3
Financial difficulties	FI	28	3

All of the scales and single-item measures range in score from 0 to 100. For global health status and functional scales, 100 is associated with a high performance while for symptoms scales, 100 is associated with high burden related to the symptoms. The calculation for each score is derived as follows.

1. A raw score is calculated as the average of the items of the scale
2. A linear transformation is applied to standardize the raw score so that the score ranges from 0 to 100.

For example, the below algorithm demonstrates how various QLQ-C30 scales are computed:

Functional scales/items:  $\text{Score} = \{1 - (\text{RS} - 1) / \text{range}\} \times 100$

Symptom scales/items:  $\text{Score} = \{(\text{RS} - 1) / \text{range}\} \times 100$

Global health status/QoL:  $\text{Score} = \{(\text{RS} - 1) / \text{range}\} \times 100$

For all scales, the Raw Score, RS, is the mean of the component items.

In case of missing items, the following rules will be applied:

1. If at least half of the items from the scale are not missing, missing items will be ignored. RS will be calculated as the mean of the non-missing items.
2. If not, the scale will be set to missing. For single item measures, the score is set to missing.

Sponsor:	Radius		
Protocol:	RAD1901-308		
Document Version No.:	1.1 (Final)	Document Date:	10-MAY-2021

QoL endpoints will be summarized by treatment at baseline and each study visit, along with CFB. Line graph presentation of arithmetic mean ( $\pm$ standard deviation) plots of scores and CFB versus time point will be produced.

Summaries of absolute and change from baseline values of each EORTC QLQ-C30 scale/item and associated 95% CI will be reported by scheduled visit for each treatment group. Line graph presentation of least square mean plots of scores versus time point will be produced.

